2.2. Study Design

This is a randomized, double-blind, placebo-controlled, parallel-group, Phase 2a study to investigate the mechanism of action of PF-04965842 by correlating efficacy outcomes with changes from baseline in key skin and blood biomarkers in adult participants ≥ 18 years of age with moderate-to-severe AD. Participants will be screened within 28 days prior to the first dose of study intervention to confirm study eligibility. A total of approximately 51 participants will be randomized in a 1:1:1 ratio to receive PF-04965842 200 mg QD, PF-04965842 100 mg QD, or matching placebo QD for 12 weeks. A study design schematic is presented in Figure 1.

Figure 1 Study Design Schematic

At the end of the 12-week study treatment, qualified participants will have the option to enter the long-term extension (LTE) Study B7451015. Participants discontinuing early from this study will undergo a 4-week off-treatment follow-up period.

Eligible participants will be randomized into 3 intervention groups in the study:

Group 1 (N=17): PF-04965842 200 mg QD taken orally for 12 weeks.

Group 2 (N=17): PF-04965842 100 mg QD taken orally for 12 weeks.

Group 3 (N=17): placebo QD taken orally for 12 weeks.

The total duration of participation in the study is up to 20 weeks, including up to 4 weeks for screening, 12 weeks study intervention, and a follow-up period of 4 weeks after study intervention (for those participants who do not enter the LTE study).

A full schedule of activities for the study is provided in Appendix 7.

Sample Size Determination

The sample size of this study is based on the objective to evaluate changes in key AD biomarkers in skin lesions, including biomarkers for general inflammation (MMP12),

hyperplasia (K16), Th2 (CCL17, CCL18, CCL26), and Th22 (S100A8, S100A9, S100A12) with PF 04965842 200 mg QD, PF 04965842 100 mg QD, and placebo.

A total sample of approximately 51 participants, with 17 participants randomized to PF-04965842 200 mg QD, 17 participants randomized to PF-04965842 100 mg QD, 17 participants randomized to matching placebo (1:1:1 randomization) is planned.

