A sample size of 17 participants per treatment group would provide about 92% chance that the 95% CI for the mean fold-change (post-baseline relative to baseline) has a half-width of no more than 3.2 (which is within 64% of an assumed maximal standard deviation of 5 for the fold-change, as based on published data). Calculations are based on the assumption of a chi-square distribution for the variance so that the width of the estimated confidence interval is a random quantity.

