5.1.1. Estimands

The primary objective of this study is to assess the effects of PF-04965842 on lesional and non-lesional skin biomarkers of adult participants with moderate-to-severe AD. A hypothetical estimand will be used for estimation. The following estimand attributes will be considered:

- Population: Participants with moderate-to-severe AD as defined by the inclusion criteria and with a valid baseline and Week 12 assessment;

- Variable: Fold-change from baseline in the biomarkers for general inflammation (MMP12), hyperplasia (K16), Th2 immune response (CCL17, CCL18, CCL26), and Th22 immune response (S100A8, S100A9, S100A12);
- Intercurrent event: All data collected will be utilized;
- Population-level summary: Mean fold-change from baseline within each treatment group.

Some secondary objectives require analyses of binary endpoints for which, a composite estimand with the following attributes will be considered:

- Population: Participants with moderate-to-severe AD as defined by the inclusion criteria and with a valid baseline;
- Variable: Binary outcome measures such as responder-based endpoints. Participants who discontinue from the study treatment for any reason are defined as non-responders after that point;
- Intercurrent event: The intercurrent event is captured through the variable definition;
- Population-level summary: Proportion of participants who are responders in each treatment group and differences in proportions of responders between each active dose and placebo.

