5.2.1. Analysis of Primary Endpoint

The population for the primary analysis will be all participants in the FAS having valid biomarker data at baseline and Week 12.

The primary endpoints in this study include mean fold-changes for the following biomarkers:

- General inflammation (MMP12);
- Hyperplasia (K16);
- Th2 (CCL17, CCL18, CCL26);
- Th22 (S100A8, S100A9, S100A12).

In each participant, expression levels from RT-PCR will be normalized to the housekeeping gene RPLP0 (validated in other studies) by negatively transforming the Ct values to $-dCt$, obtaining an equivalent to log2 scale expression values (reporting unit: log2 [Expression/RPLP0]). The expression values below detection will be estimated for each gene as the 20% of the minimum of unlogged values across all samples (which is equivalent to subtracting 2.321928 from the $-dCt$ minimum value). The expression levels below detection may provide important information about some markers that significantly change with treatment (eg, the expression may decrease below the level of detection after treatment), therefore this imputation is an important step in the analysis.

RT-PCR expression data in log2 scale will be modeled using a mixed effect model with Treatment, Time Point, and Tissue Type as a fixed effect and a random intercept for each participant. This model will yield unbiased estimates and valid inferences in the presence of a missing data mechanism that is missing at random (MAR).¹ This approach introduces less bias than restricting the analysis for participants with complete observations. Contrasts will be used to estimate the log2 fold-changes for each treatment group. Fold-changes will be computed by obtaining the antilog of log2 fold-changes. Point estimates and 95% confidence intervals (CIs) will be obtained for the fold-change from baseline in the biomarker values for each treatment group based on this model.

Correlation analyses will be performed to assess if the fold-change from baseline in biomarkers correlates with change (from baseline) in the clinical efficacy endpoints such as IGA, EASI, and Peak Pruritus NRS.

Supportive analyses for the primary endpoint will also be performed using the PPAS.

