5.2.3. Analyses of Other Endpoints

The responses based on IGA, EASI (eg, EASI-75), and severity scale of the Peak Pruritus NRS will be summarized descriptively by visit and treatment. The difference of the improvement from baseline between each PF-04965842 dose and placebo will also be derived.

If a participant withdraws from the study, then this participant will be considered a non-responder after withdrawal for any binary valued clinical efficacy endpoint.

CCI

CCI

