6.3.4. Change from Baseline in BSA%

- Summary: Change from baseline at all scheduled visits;
- Population: FAS;
- Statistical Method: Descriptive (LSmean, SD, mean difference, SE, 95% CI, median, Q1, Q3);
- Missing Data: Observed Data.

CCI [REDACTED]
[REDACTED]
[REDACTED]
[REDACTED]
[REDACTED]
[REDACTED]
[REDACTED]

C

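### The primary biomarker model gives each randomised arm its own baseline mean and so forgoes a modest, nearly free gain in precision for the lesional Week 12 fold-changes

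*SAP*

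**What the plan says.** SAP 5.2.1 fits a "mixed effect model with Treatment, Time Point, and Tissue Type as a fixed effect and a random intercept for each participant" to log2 expression, and Protocol 9.4.1 uses the same wording. Baseline is one level of Time Point, so baseline biopsies are part of the outcome. No interaction, baseline covariate or constraint on the baseline means is stated. The same paragraph says "Contrasts will be used to estimate the log2 fold-changes for each treatment group", and the estimand in SAP 5.1.1 has "Population-level summary: Mean fold-change from baseline within each treatment group". The primary analysis population is "all participants in the FAS having valid biomarker data at baseline and Week 12".

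Allocation and size are in SAP 2.2: "A total of approximately 51 participants will be randomized in a 1:1:1 ratio", with precision calculated for "A sample size of 17 participants per treatment group".

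There is no hypothesis testing (SAP 5.1), but the arms are compared. SAP 5.2.1 ends by reading each active arm's estimate and CI against placebo's. Protocol 4.1 says group differences will be estimated. SAP 6.6 plans forest plots of treatment differences from the same model.

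For the continuous clinical outcomes, SAP Appendix 1 lists MMRM for change in EASI, NRS and %BSA without naming model terms. SAP 6.3.4 gives "Descriptive (LSmean, SD, mean difference, SE, 95% CI, median, Q1, Q3" for %BSA, also without covariates.

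**The concern.** Randomisation makes the three arms' baseline means equal in expectation, and every analysed participant must have a baseline value. A model that gives each arm a free baseline mean ignores that equality. Chance imbalance at baseline then passes into the change from baseline through regression to the mean, and the intervals are wider than the data require.

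This matters most for the comparison with placebo. SAP 5.2.1 treats a fold-change seen in the active arms but not in the placebo arm as likely due to mechanism of action. With 17 per arm and eight primary biomarkers reported by interval alone, wider intervals blur that reading.

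**Working it through.** **Inputs.** From the documents: 17 per arm, three arms, 1:1:1; SD 5 and half-width 3.2 for the planning calculation (SAP 2.2, Protocol 9.2); required lesional biopsies at Weeks 0, 4 and 12 and non-lesional at Week 0; non-lesional at Week 12 optional (Protocol 4.1). Assumed: the correlation ρ between two biopsies from one participant, taken as 0.2, 0.5 and 0.8; equal variance σ² at each biopsy; and one ρ for all pairs, as a random intercept implies.

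**The plan's own figure.** With t(0.975, 16) = 2.1199, the chance that the half-width is at most 3.2 is P[χ²₁₆ ≤ 16 × (3.2√17 / (2.1199 × 5))²] = P[χ²₁₆ ≤ 24.79] = 92.6%. This agrees with the stated figure of about 92%, and 3.2/5 = 64% as stated. The calculation uses the SD of the fold-change itself, so it assumes no baseline adjustment.

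**What the written model estimates.** One simulated data set was fitted both ways, with true lesional Week 12 changes of −0.5 (placebo), −1.5 (100 mg) and −3.0 (200 mg).
- Main effects only, as written: a single Week 12 effect of −1.257 shared by all arms. No arm-specific fold-change exists.
- With arm-by-time-by-tissue cells: lesional estimates of −0.494, −1.766 and −3.206, each equal to the arm's raw mean change.
- Same model, optional non-lesional Week 12 biopsy, 100 mg arm: −0.212 from the model against −0.671 from the raw pairs. These differ because the random intercept borrows from the other biopsies.

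**Precision, lesional Weeks 0 and 12 only.** The formulas treat variances and ρ as known.
- Free baselines: within-arm variance 2σ²(1−ρ)/n; difference from placebo 4σ²(1−ρ)/n.
- Common baseline: the within-arm variance is (σ²/n)[(1−ρ²) + (1−ρ)²/3] = [2σ²(1−ρ)/n] × (2+ρ)/3. The difference from placebo is 2σ²(1−ρ²)/n = [4σ²(1−ρ)/n] × (1+ρ)/2.
- Reduction in CI width = 1 − √ratio. For example, at ρ = 0.5: 1 − √(2.5/3) = 8.7% within arm and 1 − √0.75 = 13.4% against placebo.

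**Precision, adding lesional Week 4 and baseline non-lesional.** These come from generalised least squares at 17 per arm and σ = 1, with one baseline mean per tissue type. Standard errors are free → common.

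| ρ | Within arm, Weeks 0 and 12 only | Versus placebo, Weeks 0 and 12 only | Within arm, four biopsies | Versus placebo, four biopsies |
|---|---|---|---|---|
| 0.2 | 14.4% | 22.5% | 0.307 → 0.261 (15.0%) | 0.434 → 0.331 (23.6%) |
| 0.5 | 8.7% | 13.4% | 0.243 → 0.214 (11.8%) | 0.343 → 0.280 (18.4%) |
| 0.8 | 3.4% | 5.1% | 0.153 → 0.139 (9.7%) | 0.217 → 0.184 (15.0%) |

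The extra gain in the last two columns comes from the baseline non-lesional biopsy. Adding Week 4 alone leaves the two-biopsy figures unchanged.

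**A baseline-covariate model.** If the baseline mean is treated as known, (1−ρ)²σ²/(3n) is left out of the within-arm variance. The SE is then too small by the factor √[3(1+ρ)/(4+2ρ)]: 0.905 at ρ = 0.2 and 0.949 at ρ = 0.5, or about 10% and 5% too small. The difference from placebo is unaffected, because the baseline mean cancels.

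**Selection on Week 12 data.** If keeping only participants with Week 12 data shifts one arm's baseline mean by d, with its change left the same, the common-baseline estimate for that arm is off by (2/3)(1−ρ)d. That is 0.53d at ρ = 0.2 and 0.33d at ρ = 0.5.

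**The case against.** The strongest reply is that nothing is broken. The primary summary is a within-arm mean fold-change, the sample size was set on the unadjusted fold-change, and the stated assurance reproduces. A raw change score delivers that precision without bias. This stands: a reader might infer that the trial falls short of its planned precision, and the documents do not support that.

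Second, a reader might infer that every fold-change is a raw change score whatever terms are added. That is too strong. Main effects alone give no arm-specific change, so the missing interactions are the prior defect. The result also fails for the optional non-lesional Week 12 biopsy. It holds for the required lesional contrast once the interactions are in place.

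Third, the common-baseline constraint rests on randomisation, while the primary set is selected on having Week 12 data. This also stands, and it shapes the fix.

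Fourth, the size depends on a correlation that the documents do not give, and the largest gains are for the difference from placebo, which SAP 5.2.1 assesses only informally. This is true. But Protocol 4.1 and SAP 6.6 do plan between-group estimates, and the direction of the gain holds for any ρ below 1.

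Last, one might infer that the clinical analyses exclude baseline adjustment. Appendix 1 is silent on model terms, so they are unspecified. The sentence in SAP 5.2.3, "The difference of the improvement from baseline between each PF-04965842 dose and placebo will also be derived", follows one on descriptively summarised responses and does not settle the matter.

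**Conclusion.** This is a worthwhile improvement and not an error. Once the interactions needed for a per-arm fold-change are supplied, the lesional Week 12 estimate is a raw change score that leaves baseline information unused. For ρ from 0.2 to 0.8, a common baseline mean would narrow the within-arm CI by about 14% to 3%, or 15% to 10% if the baseline non-lesional biopsy also contributes. The dose-versus-placebo CI would narrow by 22.5% to 5%, or 24% to 15%. On Weeks 0 and 12 alone, the comparison with placebo would behave as if each arm had 17/0.60 = 28 participants at ρ = 0.2, 17/0.75 = 23 at 0.5 and 17/0.90 = 19 at 0.8.

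These are relative gains under equal variances and a single correlation, both treated as known; the four-biopsy figures also need that correlation to hold across tissue types. They should not be read as absolute half-widths, because the planning SD of 5 is on the fold-change scale and the model is on log2.

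**What to change.** In SAP 5.2.1 and Protocol 9.4.1, specify log2 expression with time-by-tissue and treatment-by-time-by-tissue terms, a random intercept, and one baseline mean per tissue type common to all arms. Fit this to all FAS participants with a baseline biopsy, since equal baselines are assured only before selection on Week 12 data. This also suits the SAP's own argument that its mixed model is less biased than restricting to complete observations. Keep the unconstrained model in the Week 12 set as a sensitivity analysis.

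A model with baseline as covariate may be used for differences from placebo. It should not be offered as an equivalent for within-arm fold-change CIs unless the uncertainty in the baseline mean is included.

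In SAP Appendix 1, state the MMRM terms for change in EASI, NRS and %BSA and include the baseline value as a covariate; align SAP 6.3.4.

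The cost is SAP and protocol wording plus model code, with no new data, visits or participants. The analysis-set and estimand wording must change too (SAP 5.1.1, 5.2.1 and 6.1.1; Protocol 9.1.1 and 9.4.1), and the change should be made before unblinding. One downside should be stated in the report: within-arm fold-changes would be expressed against the pooled baseline instead of each arm's own.

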9.4.1. Analysis of the Primary Endpoint

The population for the primary analysis will be all participants in the FAS having valid biomarker data at baseline and Week 12.

The primary endpoints in this study include mean fold-changes for the following biomarkers:

- General inflammation (MMP12);
- Hyperplasia (K16);

- Th2 (CCL17, CCL18, CCL26);
- Th22 (S100A8, S100A9, S100A12).

In each participant, expression levels from RT-PCR will be normalized to the housekeeping gene RPLP0 (validated in other studies) by negatively transforming the Ct values to $-dCt$, obtaining an equivalent to log2 scale expression values (reporting unit: log2 [Expression/RPLP0]). The expression values below detection will be estimated for each gene as the 20% of the minimum of unlogged values across all samples (which is equivalent to subtracting 2.321928 from the $-dCt$ minimum value). The expression levels below detection may provide important information about some markers that significantly change with treatment (eg, the expression may decrease below the level of detection after treatment), therefore this imputation is an important step in the analysis.

RT-PCR expression data in log2 scale will be modeled using a mixed effect model with Treatment, Time Point, and Tissue Type as a fixed effect and a random intercept for each participant. This model will yield unbiased estimates and valid inferences in the presence of a missing data mechanism that is missing at random (MAR). ²⁹ This approach introduces less bias than restricting the analysis for participants with complete observations and is consistent with estimation of a hypothetical estimand. Contrasts will be used to estimate the log2 fold-changes for each treatment group. Fold-changes will be computed by obtaining the antilog of log2 fold-changes. Point estimates and 95% confidence intervals (CIs) will be obtained for the fold-change from baseline in the biomarker values for each treatment group based on this model.

Correlation analyses will be performed to assess if the fold-change from baseline in biomarkers correlates with change (from baseline) in the clinical efficacy endpoints such as IGA, EASI, and Peak Pruritus NRS.

Supportive analyses for the primary endpoint will also be performed using the PPAS.

[figure not shown]

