While statistical tests of hypotheses will not be performed to compare the fold-change from baseline in the abrocitinib groups versus placebo, the point estimates and 95% CIs for the two abrocitinib dose groups will be assessed in relation to those from the placebo group. A fold-change from baseline observed in the abrocitinib groups alone (and correlated with efficacy) but not in the placebo group is likely due to the mechanism of action of abrocitinib.

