While statistical tests of hypotheses will not be performed to compare the fold-change from baseline in the PF-04965842 groups versus placebo, the point estimates and 95% CIs for the two PF-04965842 dose groups will be assessed in relation to those from the placebo group. A fold-change from baseline observed in the PF-04965842 groups alone (and correlated with efficacy) but not in the placebo group is likely due to the mechanism of action of PF-04965842.

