6. ANALYSES AND SUMMARIES

Point estimates and 95% confidence intervals will be provided for each of the PF-04965842 QD treated groups (200 mg and 100 mg) and placebo.

A summary of analyses for clinical efficacy endpoints is provided in Appendix 1. Visit windows to be used for all efficacy analyses and some relevant safety analyses are detailed in Appendix 2.

Data collected at Week 16 will be displayed in listings only, and will not be part of any analyses, unless specifically noted otherwise.

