6.1.1. Primary Analysis

- Summary: Fold-change from baseline at Week 12;
- Population: FAS;
- Statistical Method: Estimate and 95% CI from MMRM described in [Section 5.2.1](#);
- Missing Data: No explicit imputation.

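### The primary biomarkers get within-arm fold-changes only; no overall contrast with placebo is named, although the mechanism statement depends on comparing the arms

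*SAP*

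**What the plan says.** Every passage that defines the primary output is within-arm.

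- Estimand (SAP 5.1.1): "Population-level summary: Mean fold-change from baseline within each treatment group".
- Model (SAP 5.2.1): log2 expression is "modeled using a mixed effect model with Treatment, Time Point, and Tissue Type as a fixed effect and a random intercept for each participant". No interaction is named.
- Contrasts (Protocol 9.4.1, same text in SAP 5.2.1): "Contrasts will be used to estimate the log2 fold-changes for each treatment group".
- Output (SAP 6.1.1): "Summary: Fold-change from baseline at Week 12". SAP 6 adds: "Point estimates and 95% confidence intervals will be provided for each of the PF-04965842 QD treated groups (200 mg and 100 mg) and placebo".

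SAP 5.2.1 then credits one pattern of results to how the drug works: "A fold-change from baseline observed in the PF-04965842 groups alone (and correlated with efficacy) but not in the placebo group is likely due to". Protocol 9.4.1 carries the same sentence with the drug's name in place of its code.

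The plan does intend some comparison. The sentence before the mechanism statement says that the active estimates and CIs will be judged against those from placebo. Protocol 4.1 says in general terms that differences between groups will be estimated and not tested. Neither names a statistic for the primary genes. Elsewhere the plan is explicit: the binary-endpoint estimand in SAP 5.1.1 includes "differences in proportions of responders between each active dose and placebo", and SAP 5.2.3 derives differences from placebo for IGA, EASI and pruritus. SAP 6.6 plans plots of between-group differences, but only by subgroup and for endpoints labelled co-primary, a label that SAP Appendix 1 attaches to IGA and EASI-75.

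**The concern.** A change that is visible in one arm and not in another is not an estimate of the difference between them. The mechanism statement leaves open what counts as an observed change, and it gives no reading for the case where placebo also changes.

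Some change in all arms is plausible. The target lesion is chosen at baseline and the same area is biopsied again even if it has cleared (Protocol 8.1.2). In Phase 2b, 15.7% of placebo participants reached the 4-point itch response at Day 15 (Protocol 2.2.2). That is an itch result, not lesional gene expression at Week 12, so it shows only that placebo participants can improve.

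At stake is how the primary biomarkers are linked to the drug's mechanism, which is the purpose of the study (Protocol 4.2). A shared change could be credited to the drug, or a real effect could be missed because placebo moved too.

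**Working it through.** **1. The plan's own figure.** Inputs from Protocol 9.2 and SAP 2.2: 17 per arm, SD 5, half-width 3.2. With t(0.975, 16 df) = 2.120, P(half-width ≤ 3.2) = P(χ²₁₆ ≤ 16 × (3.2 × √17 / (2.120 × 5))²) = P(χ²₁₆ ≤ 24.8) = 92.6%. This matches the stated 92% and is a one-arm figure.

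**2. No drug effect.** Assume the same true change d (in SDs of the log2 change) in all arms, normal data, independent arms, and an observed change meaning a 95% CI that excludes no change. The documents give neither d nor this definition. Then p = P(noncentral t, 16 df, noncentrality d√17, exceeds 2.120), and the both-doses-not-placebo pattern has probability p² × P(placebo CI covers no change). The last column is simulated.

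| d | p | Placebo CI covers no change | Pattern | Pattern, and placebo estimate outside both active CIs |
|---|---|---|---|---|
| 0.2 | 0.118 | 0.88 | 1.2% | |
| 0.33 | 0.248 | 0.75 | 4.6% | 1.0% |
| 0.5 | 0.491 | 0.51 | 12.3% | 1.8% |
| 0.6 | 0.642 | 0.36 | 14.8% | 1.9% |
| 0.8 | 0.872 | 0.13 | 9.7% | 1.7% |
| 1.0 | 0.972 | 0.03 | 2.7% | |

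A direct contrast (pooled SD, 48 df) favours both doses in 0.5% of such trials. The plan also requires correlation with efficacy. In simulations that assume a 1.5 SD efficacy shift in both active arms and a nominally significant correlation, the 12.3% at d = 0.5 becomes 0.3-1%, 5-9% or about 12% at a within-participant correlation of 0, 0.3 or 0.6.

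**3. True effect of 1 SD at both doses.** Active arms change by d + 1, placebo by d. At d = 0: 0.972² × 0.95 = 90%. At d = 0.33, 0.5 and 0.8 the active CIs almost always exclude no change, so the pattern is close to the placebo column: 75%, 51% and 13%. Adding the correlation condition at 0.6 leaves these at 89.5%, 74.8%, 51.0% and 13.0%. The direct contrast excludes a ratio of 1 for both doses in about 71% throughout.

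**4. One worked case.** Assume a log2 SD of 1.5 (not given in the documents). The within-arm half-width is 2.120 × 1.5/√17 = 0.771. Log2 changes of −0.871 (active) and −0.671 (placebo) give fold-changes 0.55 (0.32 to 0.93) and 0.63 (0.37 to 1.07). Read separately, only the active arm changed. The ratio is 2^(−0.2) = 0.87, with half-width 2.037 × 1.5 × √(2/17) = 1.048 on the log2 scale, so 0.42 to 1.80.

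**5. The model terms.** With main effects only, expected log2 expression is a constant + treatment + time + tissue. Week 12 minus baseline in lesional skin is then time(12) − time(0), the same for every arm. Arm-specific fold-changes need Treatment by Time Point terms.

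**6. Precision of a contrast.** Within arm, the half-width is 2.120/√17 = 0.51 SD. Against placebo it is 2.011 × √(2/17) = 0.69 SD (48 df) or 2.037 × √(2/17) = 0.70 SD (32 df). On the plan's raw scale at SD 5 these are 2.57 and 3.45-3.49. P(half-width ≤ 3.2) for the contrast is P(χ²₃₂ ≤ 26.9) = 27.5% or P(χ²₄₈ ≤ 41.3) = 25.9%.

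**The case against.** The within-arm estimand is deliberate. It is stated consistently, the study is sized for it, and between-group tests are ruled out. The mechanism wording is hedged and drives no decision. A reader could also approximate the ratio from the arm estimates and CIs. All of this stands, and it is why the within-arm results should be kept. It does not rule out a contrast, because a ratio with a CI is estimation.

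The strongest point is that the plan says the active results are judged against placebo. If that means placebo's estimate must lie outside both active CIs, the false pattern drops to about 1-2%; if the CIs must not overlap, to 0.03% or less. This answers most of the first risk, though the documents do not say which reading applies. It does not help with the second: an added condition can only lower the 51% and 13%.

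A reader might infer more than the documents support:

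- That the SAP dropped a placebo ratio promised in Protocol 4.1. That sentence names neither the endpoint nor a ratio.
- That the model would force every placebo ratio to 1. This is true of the listed terms taken literally, but the same paragraph asks for a fold-change in each treatment group, so arm-specific terms are evidently intended. This is a wording gap.
- That the plan has a 12-15% error rate. Those figures need a shared change near 0.5-0.6 SD, an assumed definition of observed, and either no correlation condition or a strong within-participant correlation.

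**Conclusion.** The point holds as a gap in estimation and interpretation, and it should be fixed. No overall active-versus-placebo contrast is named for the eight primary genes, and SAP 5.2.1 and 6.1.1 show no redaction where one would sit. The mechanism reading therefore rests on separate one-sample results.

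The risk of false attribution is modest and depends on how the statement is read. It is small for a shared change of about 0.2 SD or less or 1 SD or more. The loss when placebo really changes is the firmer problem. The pattern beats the contrast only when placebo changes little: 90% against 71% at no placebo change, and about equal at 0.33 SD. All sizes are illustrative, because the documents give no log2 SD, no placebo change and no definition of observed or correlated.

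This is not a type I error breach, since no test is planned. Nor can one say that the plan contains no such contrast anywhere: the supplementary biomarker SAP mentioned in the SAP version history and the redacted biomarker text cannot be seen.

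**What to change.** In SAP 5.2.1 and 6.1.1, Protocol 9.4.1 and the estimand summary:

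- State the Treatment by Time Point terms within tissue type in the model.
- Add, for each biomarker and dose, the Week 12 lesional ratio of fold-changes versus placebo (difference in log2 change, antilogged) with a 95% CI, as estimation only and without a test.
- Base the mechanism statement on that ratio, and keep the within-arm fold-changes as descriptive.
- In the sample size text, note that the 92% applies to the interval for a single arm.

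This takes wording and two contrasts per biomarker, with no new data. SAP 2 says that major changes to the primary analysis are also reflected in a protocol amendment, so a short one may be needed. The real price is the wider interval in step 6: the contrast meets the plan's 3.2 half-width with only 26-28% probability, and at 17 per arm the half-width met with 92% probability is about 3.9-4.1. That width is the actual uncertainty about the drug's contribution, and the plan should show it.
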